#### Secondary Outcome Definitions:

**Hypoxia, hypotension or need for advanced airway:** The principal safety outcome for the trial will be the incidence of serious adverse events following the first dose of analgesic following randomization including hypoxia (SpO2 < 90%), hypotension (SBP < 90 mmHg) or the need for advanced airway management (placement of an endotracheal tube, supraglottic airway or bag mask ventilation) until ED discharge (up to 120 minutes), when feasible.

Composite outcome of nausea, vomiting, headache, and/or dizziness requiring treatment: The incidence of nausea, vomiting, headache, and/or dizziness requiring treatment will be recorded for initial 30 minutes, when feasible.

Verbally administered Numeric Rating Scale (VNRS) pain measurements (0-100) at 30- minute intervals: VNRS for clinical pain (0-100) measurements at approximate 30-minute intervals until discharge from the ED (up to 120 minutes) or rescue narcotic administration, will be obtained when feasible.

**Patient Global Assessment (PGA) of Pain Control at 30-minute intervals:** The PGA of the method of pain control at approximate 30-minute intervals until discharge from the ED (up to 120 minutes) or rescue narcotic administration, will be obtained when feasible. The research team will read the following statement aloud to the subject and the response will be recorded: "Overall, would you rate this method of pain control during the last 30 minutes/hours as being poor (1), fair (2), good (3), or excellent (4)?"

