## IX. Human Subjects

We anticipate that this study will be conducted utilizing a written informed consent while the patient resides in the ED.

Study Risks and Benefits: Risks associated with pain management include allergic reaction, hypoxia requiring oxygen, (SPO2 < 90%), hypotension (SBP < 90 mmHg), or need for advanced airway management (placement of an endotracheal tube or supraglottic airway) following medication administration.

Regardless of treatment arm, we anticipate that enrolled subjects will benefit from increased monitoring of primary and secondary outcomes, specifically, a focus on adequate pain control and pain management complications including respiratory compromise, hypotension, decreased sensorium, and need for advanced airway control.

Institutional Review Board: A central IRB at the University of Pittsburgh will be utilized for the regulatory needs of studies. All current LITES Network sites have IRBs which have experience and engagement with central IRB procedures.

Training and Participating Site Coordination: As the clinical coordinating center for the trial, the University of Pittsburgh (LITES) at the University of Pittsburgh will be collaboratively responsible for all research coordinator training, provider training. Research coordinators, providers and associated staff will be trained during the months prior to the trial start date regarding the scientific basis for the study, specific inclusion and exclusion criteria, study procedures and SOPs. Training verification and retraining will occur if new staff is hired at individual participating sites.

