- i. Unanticipated Problem Involving Risk to Subjects or Others (UPIRTSO) refers to any accident, experience, or outcome that meets the following criteria: unexpected in terms of nature, severity or frequency; related, or possibly related, to a subject's participation in research; and places subjects or others at greater risk of harm (including physical, economic, or social) than was previously known or recognized.

Assessing and Reporting Adverse Events (AEs) and Non-compliance: Adverse events will be reviewed by the study sites and assessed for relationship to the study intervention. Investigators and study team will determine if any related adverse events occur during the period from enrollment through study participation termination. If reportable adverse events occur, they will be recorded on the adverse event case report form in the electronic data capture system, which will be submitted to the Coordinating Center. All reported adverse events will be classified by: a) Severity (fatal or life-threatening, serious, or non-serious); and b) Expected vs. Unexpected. An event will be determined to be unexpected if it is not consistent with the risks identified in the package insert or with the information provided in the general investigational plan. Please refer to the table below for timelines for reporting.

This study population is expected to have a relative low number of serious adverse events but will include death from trauma related injuries. Expected adverse events that are related or possibly related to the intervention will be documented and reviewed for changes in nature, severity, or frequency across the study population.

Organization	Unexpected, fatal or life-threatening suspected adverse reactions	Unexpected, serious, suspected adverse reactions	Expected adverse reactions	Reportable non- compliance	UPIRTSO
IRB	24 hours	10 working days	No reporting	10 working days	10 working days
Dept. of Defense	30 calendar days	30 calendar days	No reporting	30 calendar days**	30 calendar days*
DSMB	24 hours	7 calendar days	At next meeting (every 6 months)	At next meeting (every 6 months)	14 days*

\*reported based on IRB determination that event is UPIRTSO \*\*reported based on IRB determination that non-compliance is serious or continuing

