Data Safety Monitoring Board (DSMB): A Data and Safety Monitoring Board (DSMB) will be created to review this study and provide recommendations regarding study continuation to the Sponsor. After initial approval and at periodic intervals (to be determined by the committee) during the course of the study, the DSMB responsibilities are to:

a. Review the research protocol, informed consent documents and plans for data and safety monitoring;

b. Evaluate the progress of the study, including periodic assessments of data quality and timeliness, participant recruitment, accrual and retention, participant risk versus benefit, adverse events, unanticipated problems, performance of the trial sites, and other factors that can affect study outcome;

c. Consider factors external to the study when relevant information becomes available, such as scientific or therapeutic developments that may have an impact on the safety of the participants or the ethics of the study;

d. Review clinical center performance, make recommendations and assist in the resolution of problems reported by the study site Investigators;

e. Protect the safety of the study participants;

f. Report on the safety and progress of the study;

g. Make recommendations concerning continuation, termination or other modifications of the study based on the observed beneficial or adverse effects of the treatment under study;

h. Monitor the confidentiality of the study data and the results of monitoring;

i. Assist by commenting on any problems with study conduct, enrollment, sample size and/or data collection.

j. The DSMB will include experts in emergency medicine, surgery (trauma/critical medicine), bioethics and biostatistics. Members will consist of persons independent of the investigators who have no financial, scientific, or other conflict of interest with the study. Written documentation attesting to absence of conflict of interest will be required.

k. The University of Pittsburgh Office of Clinical Research, Health Sciences will provide the logistical management and support of the DSMB. A safety officer (chairperson) will be identified at the first meeting. This person will be the contact person for serious adverse event reporting. Procedures for this will be discussed at the first meeting.

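### The safety reporting table gives no expedited DSMB timeline for life-threatening or serious reactions classed as expected, and the trial's principal safety events can be classed that way

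*Combined protocol and SAP*

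**What the plan says.** Section X (Assessing and Reporting Adverse Events and Non-compliance) has every reported event classified by "a) Severity (fatal or life-threatening, serious, or non-serious); and b) Expected vs. Unexpected". The reporting table that follows has two fast columns for reactions:

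- "Unexpected, fatal or life-threatening suspected adverse reactions": DSMB 24 hours, IRB 24 hours.
- "Unexpected, serious, suspected adverse reactions": DSMB 7 calendar days, IRB 10 working days.

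A single column covers expected adverse reactions, with no split by severity. Its DSMB entry is "At next meeting (every 6 months", and its IRB and Department of Defense entries are no reporting.

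On what counts as unexpected, the same section states: "An event will be determined to be unexpected if it is not consistent with the risks identified in the package insert", or with the information in the general investigational plan. Item (e) of the definitions list names the same two sources but joins them with *and*.

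Section IX (Study Risks and Benefits) gives the risks of pain management as allergic reaction, hypoxia requiring oxygen, "hypotension (SBP < 90 mmHg), or need for advanced airway management", the last explained as an endotracheal tube or supraglottic airway. Section IV (Secondary Outcome Definitions) says: "The principal safety outcome for the trial will be the incidence of serious adverse events following the first dose of analgesic", and names hypoxia, hypotension and advanced airway management, there including bag mask ventilation.

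On the safety officer (the DSMB chair), Section X (DSMB) says: "This person will be the contact person for serious adverse event reporting". The procedures are left to the DSMB's first meeting.

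**The concern.** Two classification axes create a cell for reactions that are both expected and life-threatening or serious. The table gives that cell no timeline of its own, so it falls into the column written for all expected reactions. The harms most likely to land there are the ones the trial names as its principal safety outcome, because the protocol lists most of them as known risks.

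At stake is timing. Section VI (Interim Analyses) has the DSMB weigh safety outcomes by treatment group when it considers recommending termination. It cannot weigh an event it has not received, and enrolment continues in the meantime.

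**Working it through.** No power or alpha figure is involved. The check traces one event through the text and then sizes the delay.

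**Step 1. Can a principal safety event be classed as expected?**

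| Component of principal safety outcome (Section IV) | In the Section IX risk list? |
|---|---|
| Hypoxia, SpO2 < 90% | Yes, as hypoxia requiring oxygen |
| Hypotension, SBP < 90 mmHg | Yes |
| Endotracheal tube or supraglottic airway | Yes |
| Bag mask ventilation | No |

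If Section IX counts as part of the general investigational plan, the first three can be judged consistent with listed risks. Neither definition of unexpected mentions severity. The definition of an unanticipated problem involving risk to subjects or others (UPIRTSO), in the same section, does mention it.

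**Step 2. Follow the event through the table.** Take an intubation that the investigator judges drug-related and life-threatening.

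| Label | DSMB | IRB |
|---|---|---|
| Unexpected | 24 hours | 24 hours |
| Expected | next meeting, every 6 months | no reporting |

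The event and its severity are the same; only the expectedness label changes the route.

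**Step 3. Check the other routes to the DSMB.**

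- *Safety officer (Section X, DSMB).* The role is not limited to unexpected events, but no procedure or deadline is written.
- *Emergency meeting (same section).* The chair may call one at any time, but must first know of the event.
- *Ad hoc safety review (Section VI, Interim Analyses).* It is triggered by unexpected safety concerns.
- *UPIRTSO (Section X).* It covers unexpected severity or frequency, but also requires greater risk than previously known. The DSMB's 14 days depend on an IRB determination, and expected reactions have no routine IRB report.
- *Review of expected related events for changes in nature, severity or frequency (Section X).* No reviewer or deadline is named.

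**Step 4. Size the delay.** Inputs are about 150 patients randomised 1:1 in a 3-year study (Section III) and the table's 6-month interval. Accrual is assumed to be even.

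Patients enrolled in one interval = 150 / accrual months × 6; half of them are on DSUVIA.

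| Accrual period | Enrolled in 6 months | On DSUVIA |
|---|---|---|
| 36 months (study duration) | 150 / 36 × 6 = 25 | 12.5 |
| 24 months (assumed) | 150 / 24 × 6 = 37.5 | 18.75 |
| 18 months (assumed) | 150 / 18 × 6 = 50 | 25 |

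These are maxima. An event is equally likely to fall anywhere between meetings, so the average wait is 6 / 2 = 3 months. At 36-month accrual that is 25 / 2 = 12.5 patients, 6.25 of them on DSUVIA.

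**The case against.** The strongest reply is that the table is not the whole safety system. The safety officer is the contact for serious adverse events without restriction to unexpected ones, and the procedure is to be discussed at a meeting held before the study starts. Emergency meetings are available at any time. Listed events of unlisted severity can meet the first UPIRTSO criterion. Reportable events also go on a case report form to the Coordinating Center. This defeats one inference a reader might draw, that such an event reaches the DSMB *only* at the next six-monthly meeting. What remains is that none of these routes carries a written deadline that assures prompt notice. Nor does the safety officer clause contradict the table; it defers a procedure.

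A reader might also infer that a *fatal* drug reaction takes the slow route. The documents do not support that well. Death is not in the Section IX list, so a site could reasonably find a fatal reaction inconsistent with the listed risks and report it within 24 hours. Section X does anticipate deaths, but from the trauma itself. The intubation example is stronger because intubation is listed.

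Expectedness also rests on the package insert, which is not in the documents, and on treating Section IX as part of the general investigational plan, which is an inference. So a site *could* class these events as expected; the documents do not show that it would. The differing *and* and *or* in the two definitions leave room for sites to differ, which is itself a reason to settle the rule.

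Finally, it is tempting to size the harm by event counts. An assumed 1% to 5% rate among 75 DSUVIA patients gives 0.75 to 3.75 events. That would count every principal safety event, including any brief SpO2 below 90%, and not the life-threatening or serious subset, for which the documents state no rate. Section II reports respiratory depression and hypoxia below 1%. No count is relied on here.

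**Conclusion.** The point holds as a gap in a stated rule. The table has no expedited DSMB timeline for life-threatening or serious suspected reactions classed as expected. The protocol's own risk list allows most principal safety events to be classed that way, and no other route in the plan assures prompt notice. The possible delay is 0 to about 6 months, with up to about 25 patients (12 to 13 on DSUVIA) enrolled meanwhile at even accrual over 36 months, and more if accrual is faster.

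This assumes that sites judge expectedness by type of event, that Section IX counts as part of the general investigational plan, and that the DSMB meets every 6 months. The last is not settled: the table says 6 months, while the DSMB text leaves meeting frequency to the first meeting. The documents do not show that notification would fail in practice. It should be fixed, with moderate confidence.

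**What to change.** In the DSMB row of the Section X table, apply the existing 24-hour limit to all fatal or life-threatening suspected reactions and the existing 7-calendar-day limit to all serious ones, whether expected or not. Keep the next-meeting listing for non-serious expected reactions. Add one sentence saying that a principal safety event that meets the Section X definition of life-threatening or serious follows these limits, and write the safety officer's procedure to match. While editing, use one definition of unexpected in both places and reconcile the two statements on DSMB meeting frequency.

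The IRB and Department of Defense rows need not change for this purpose; the documents do not set out the requirements behind them.

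The cost is one table row, a sentence and a few extra notices to the DSMB chair, in a trial whose protocol expects relatively few serious adverse events.

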## XI. Quality Control, Assurance and Confidentiality

[figure not shown]
Protocol Compliance: The participating study site Investigators will not deviate from the protocol for any reason without prior written approval from the IRB except in the event of the safety of the research subject. In that event, the study site Investigator will notify the reviewing IRB immediately, if possible, and request approval of the protocol deviation, or, if prospective IRB approval is not possible, the study site Investigator will notify the reviewing the respective protocol deviation. The study site Investigator will inform the reviewing IRB of all protocol deviations and unanticipated events involving risks to the research subjects and others, and will obtain prospective IRB approval for all proposed protocol changes. Persistent or serious noncompliance may result in termination of the study site's participation in the research study.

Protocol Deviations: Due to the relative focused inclusion criteria and the short intervention period, we expect few protocol deviations as compared to other large multicenter trials. If monitoring reports demonstrate evidence of continuing protocol deviations, we will analyze them to determine if they are site specific or common across the study. We will note if specific inclusion or exclusion criteria are being misinterpreted, if a certain time point in testing is being omitted, or if a common set of data elements are missing. If the deviations are site specific, retraining will be done at the site. If the problems are study wide, we will discuss them with the other investigators, the DoD and the IRB to see if the protocol needs to be amended or recruitment put on hold.

Privacy and Confidentiality: The study site Investigator's and members of their research team will make reasonable effort to ensure the research subjects' confidentiality. Subject name and other identifiable information will be kept in a secure, locked, limited access area.

Investigator Responsibilities: The study site Investigators will agree to implement the IRB approved protocol and conduct the study in accordance the ICH GCP Guidelines (E6, Section 5) as well as all applicable national, state and local laws. The study will be performed in accordance with ethical principles that have their origin in the Declaration of Helsinki and are consistent with ICH/Good Clinical Practice, and applicable regulatory requirements.

Time Table:

